Investigators will be trained in pairs to assess performance from a pre-defined set of explicitly defined metric events reliably (inter-rater reliability > 0.8). They will be blinded as to the identity of the trainee performing the procedure, how they were trained (i.e., group) and procedure order.

Procedure performance assessment

[figure not shown]
We will record how long subjects took to perform the procedure, the number of steps correctly completed and procedure errors/deviations from optimal performance. We will also record and cost the instrumentation/needles/suture etc utilised in the performance of the procedure.

Baseline Assessment: -Prior to the commencement of education and training protocol all subjects from both groups will be assessed on their performance of the VUA task. Performance on the procedure will be video recorded and assessed as previously described.

Statistical Analysis: From previous similar studies, it has been found that data has been reasonably normally distributed and suitable for parametric statistical analysis. If the data violates any of the assumptions of normality, data will be compared for statistical significance with Mann-Whitney U for comparison between two independent samples and Wilcoxon signed-rank test. Where data are normally distributed with approximately equal variance differences between groups, task performance will be compared for statistical significance with two-factor Analysis of Variance where factor one is the type of training subjects received and factor two is the order the task was performed (i.e, baseline

performance and end of training performance). The same analysis will be used to assess the binary checklist metric scores and the GEARS scores (seperately) for the Standard trained and the PBP trained groups. Specific post hoc statistical contrasts between surgeon groups performance within a training condition (i.e., between the objectively assessed performance of urology, surgery and gynecology residents) will be done with Scheffe F-tests.

Statistical power calculation: A pilot study has shown that novices on average make 16.6 (SD = 4) performance errors on the task. Assuming a reduction of ~40% with PBP training (i.e., 16.6 vs 10 errors) with a standard deviation of n = 4, an Alpha – 1% with 16 subjects in each group would yield a statistical power of 0.998 for the proposed study.

* By assessors blinded to group membership and procedure order (first or last procedure)

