** Matching according to specialty

Figure 1. the design of the prospective randomized study to evaluate the impact of PBP on learning the robotic surgical skills for a vesico-urethral anastomis (VUA) on a chicken model.

Hypothesis

- H₁ Implementation of PBP training in teaching the robotic suturing of VUA leads to better surgical training outcomes (i.e., lower number of performance errors) when compared to Halsted's method.
- H₀ There will be no difference in the procedure knowledge prior to VUA training
- H₀ There will be no difference in the objectively assessed procedure performance of the urology, surgery and gynecology residents at the end of training in the PBP group
- H₀ There will be a difference in the objectively assessed procedure performance of the urology, surgery and gynecology residents at the end of training in the Traditional trained groups.
- H₀ There will be no difference in student satisfaction with the two approaches to training.

Depth perception				
1	2	3	4	5
Constantly overshoots target, wide swings, slow to correct		Some overshooting or missing of target, but quick to correct		Accurately directs instruments in the correct plane to target
Bimanual dexterity				
1	2	3	4	5
Uses only one hand, ignores nondominant hand, poor coordination		Uses both hands, but does not optimize interaction between hands		Expertly uses both hands in a complementary way to provide best exposure
Efficiency				
1	2	3	4	5
Inefficient efforts; many uncertain movements; constantly changing focus or persisting without progress		Slow, but planned movements are reasonably organized		Confident, efficient and safe conduct, maintains focus on task, fluid progression
Force sensitivity				
1	2	3	4	5
Rough moves, tears tissue, injures nearby structures, poor control, frequent suture breakage		Handles tissues reasonably well, minor trauma to adjacent tissue, rare suture breakage		Applies appropriate tension, negligible injury to adjacent structures, no suture breakage
Autonomy				
1	2	3	4	5
Unable to complete entire task, even with verbal guidance		Able to complete task safely with moderate guidance		Able to complete task independently without prompting
Robotic control				
1	2	3	4	5

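### The test of H1 depends on an undefined normality check that switches between two different analyses; one baseline-adjusted analysis should be fixed in advance.

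*Combined protocol and SAP*

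**What the plan says.** H1, in the Hypothesis section, is one between-arm claim: PBP "leads to better surgical training outcomes (i.e., lower number of performance errors) when compared to Halsted's method". No analysis is labelled primary, so the relevant analysis is whichever one tests H1.

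The Statistical Analysis paragraph expects, from similar studies, that "data has been reasonably normally distributed and suitable for parametric statistical analysis". It then gives two branches:

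- **Normality fails.** "If the data violates any of the assumptions of normality, data will be compared for statistical significance with Mann-Whitney U". Alongside this rank comparison of the arms, the plan names the signed-rank test, without saying what it is applied to.
- **Normality holds and variances are similar.** "Where data are normally distributed with approximately equal variance differences between groups", a two-factor ANOVA is used, in which "factor one is the type of training subjects received and factor two is the order the task was performed" (baseline or end of training).

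The same scheme serves the checklist metrics and the GEARS scores, each analysed separately. The Baseline Assessment paragraph has every participant in both arms perform the task before training. The Summary and the note to Figure 1 make specialty the balancing factor for allocation.

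**The concern.** Four things are left open.

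1. **The trigger.** No diagnostic, significance level or variable is named for the normality check. Two analysts could apply it differently to the same data.
2. **The parametric branch.** The ANOVA yields a main effect of training and a training-by-order interaction. These are different contrasts, and the plan does not say which one tests H1.
3. **The fallback branch.** Mann-Whitney could be run on final or change scores; the plan does not say. The signed-rank test is for paired data, so its natural use here is before versus after within an arm, which does not compare the arms. As written, no fallback step brings baseline into the between-arm comparison.
4. **A gap between the branches.** The ANOVA needs normality and similar variances, whereas the fallback is triggered only by non-normality. Normal data with unequal variances are literally not covered.

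At stake is what the H1 result estimates, how much discretion remains once the data are seen, and whether the baseline measurement is used well. Errors and GEARS could also end up analysed by different methods.

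**Working it through.** **Inputs from the documents.** Novices: "novices on average make 16.6 (SD = 4) performance errors on the task". The planned PBP mean is 10, so the gap is 16.6 − 10 = 6.6. Alpha is 1%, with sidedness not stated. The power paragraph uses 16 per group; the Subjects section plans 18 per arm.

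**Assumptions not in the documents.** A gap of 3.3 (half the planned one), baseline-to-final correlation ρ of 0.3 to 0.5, and a Shapiro-Wilk rule at 5% as the normality check.

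**The plan's own power figure (0.998).** For two means, the noncentrality is gap / (SD × √(2/n)).
- n = 16: 6.6 / (4 × √(2/16)) = 6.6 / 1.414 = 4.67. Two-sided 1% power is 0.982 by the normal approximation and 0.966 by the t-test.
- n = 18: 6.6 / (4 × √(2/18)) = 6.6 / 1.333 = 4.95. Power is 0.991 and 0.983.

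The stated 0.998 is somewhat optimistic for a two-sided 1% test, but power is high either way. The calculation compares two means; it reflects neither the ANOVA nor baseline.

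**Which SD each analysis works with.** With 18 per arm, √(2/18) = 1/3, so the noncentrality is 3 × difference / SD.
- Interaction (change scores): SD = 4√(2(1 − ρ)), which is 4.73 at ρ = 0.3 and 4.00 at ρ = 0.5.
- Main effect of training: the mean of the two sessions has SD = 4√((1 + ρ)/2), which is 3.22 and 3.46. The difference is halved, because the arms are expected to be equal at baseline.
- ANCOVA: SD = 4√(1 − ρ²), which is 3.82 and 3.46.

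**Power, two-sided 1%, 18 per arm, SD 4** (noncentral t or simulation; where two values are shown, separate runs with and without rounding to whole errors gave slightly different results):

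| Analysis | Gap 6.6, ρ 0.3 | Gap 6.6, ρ 0.5 | Gap 3.3, ρ 0.3 | Gap 3.3, ρ 0.5 |
|---|---|---|---|---|
| ANOVA main effect | 0.63 | 0.56 | 0.13 | 0.11 |
| ANOVA interaction | 0.92 | 0.98 | 0.27–0.28 | 0.41 |
| Mann-Whitney, final scores | 0.97 | 0.97 | 0.37 | 0.36–0.37 |
| ANCOVA | 0.99 | 0.998 | 0.42–0.45 | 0.53–0.54 |

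The two branches (interaction versus Mann-Whitney on final scores) reach different decisions at 1% in about 30% to 33% of trials at gap 3.3. At gap 6.6 they differ in 8% (ρ = 0.3) and 4% (ρ = 0.5).

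**How often normal data would trigger the fallback.** Checking two cells (each arm's final scores): 1 − 0.95² = 9.8%. Checking four arm-by-order cells: 1 − 0.95⁴ = 18.5%. Four cells with scores rounded to counts: 22% to 25% in simulation. The range of about 10% to 25% is itself a result of the missing criterion.

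**Type I error at nominal 1%.** Choosing between the interaction and Mann-Whitney by the normality check gave 0.7% to 1.2%, within simulation error. With one arm's SD at 0.5 or 0.33 of the other's, the pooled t-test gave 1.15% to 1.19%. With data skewed enough to fail the check in about 91% of trials, ANCOVA gave 0.7% to 0.8%, so it did not need normality to hold its level.

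**Robust standard errors as the main analysis.** At gap 3.3 and ρ = 0.5, HC3 lowers ANCOVA power from about 0.53 to 0.46.

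**The case against.** The rule is written in advance, the authors expect normal data, and the fallback is only a contingency. At the effect the trial is powered for, Mann-Whitney on final scores has about 0.97 power, so a switch would rarely change the answer. The 3.3 gap, the correlation and the Shapiro-Wilk rule are all assumptions. All of this stands, and it limits the weight of the point. It does not supply the missing criterion, ANOVA term or score.

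A reader might infer more than the documents support:

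- **That choosing the test from the data inflates false positives.** The simulations show no such inflation.
- **That the fallback is incapable of testing the interaction or using baseline.** Mann-Whitney on change scores would do both, and the signed-rank test uses baseline within an arm. The plan simply does not say that change scores will be used.
- **That switching to ranks costs a great deal of power.** Compared with the planned interaction test, at gap 3.3 it loses about 4 to 5 points at ρ = 0.5 and gains about 9 to 10 at ρ = 0.3. The larger shortfall is relative to ANCOVA, which is in neither branch.
- **That unequal variances are a serious hole.** The gap is literal, but at 18 versus 18 its effect on error rates is slight. The plan itself assumes SD 4; a narrower PBP spread after training to a benchmark is plausible but is an inference.
- **That within-arm signed-rank results will be offered as proof of H1.** The plan does not say so; it only leaves their role unstated.

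**Conclusion.** The point holds as a should-fix matter of specification and efficiency, not as a threat to validity. The test of H1 turns on a check with no criterion and leads to analyses that answer different questions, with the ANOVA term and the Mann-Whitney score unspecified. The unnamed ANOVA term matters even at the planned gap: at ρ of 0.3 to 0.5 the interaction has power 0.92 to 0.98 and the main effect 0.63 to 0.56.

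If the true gap is about half the planned one, the two branches disagree in roughly three trials in ten. ANCOVA then has power 0.42 to 0.53, against 0.37 for Mann-Whitney and 0.27 to 0.41 for the interaction. That gain comes from replacing either planned branch, not from avoiding the switch. These sizes rest on SD 4 in both arms, 18 per arm, two-sided 1% and the assumed gap and correlations. The trigger rate of 10% to 25% rests on an assumed rule.

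**What to change.** State one analysis for H1, to be used whatever a normality check shows: ANCOVA of the end-of-training error count by arm, adjusted for baseline errors and specialty, with conventional standard errors. Report the adjusted difference with its confidence interval, and state the alpha and its sidedness.

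List a rank test or a permutation test stratified by specialty, and optionally robust standard errors, as sensitivity analyses only. HC3 should not be the main analysis, because at this sample size it costs power to address a problem that is nearly harmless with equal arms. State that within-arm signed-rank tests are descriptive and are not evidence for H1.

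The cost is SAP wording, a short sensitivity run and three degrees of freedom for the covariates (one for baseline, two for specialty: residual 36 − 2 = 34 becomes 31). No extra participants or measurements are needed.

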PROVESA trial

Proficiency based progression training for robotic vesico-urethral anastomosis chicken model versus the Halsted's model: a cross-specialty, multicentric, randomized and blinded clinical trial.

Study Protocol

Principal Investigator: [name] [name]

Research center: ORSI Academy, Melle, Belgium

July 27th 2020

NCT ID not yet assigned

Ethical Committee approval number 22072020

Summary

In a prospective, randomized and blinded study robotic naïve (urology ($n = 12$), surgery ($n = 12$) and gynecology ($n = 12$)) residents ($n = 36$) from the KU Leuven and University of Gent residency training programs will be randomized (in equal discipline numbers) to Traditional Halstedian apprenticeship type training or proficiency based progression (PBP) training to learn to perform a vesico-urethral anastomosis (VUA) on a chicken model. Both groups will receive the same e-learning (on how to perform the VUA on the chicken model) and skills laboratory robotic training curriculum. The PBP trained group will however be required to demonstrate quantitatively defined proficiency benchmarks for training progression (i.e., from e-learning to the skills lab). The PBP group will also have a defined benchmark to demonstrate before training is deemed completed. The Traditional trained group will train in the same skills laboratory for a case-matched period of time as the PBP group, with the same level of supervising faculty proctors and using the same training resources but with no proficiency benchmarks or metric-based feedback. Both groups will be required to perform a VUA on the chicken model before skills training proper and at the end of training. Investigators will be trained in pairs to assess VUA performance from a pre-defined set of explicitly defined binary metric events reliably (inter-rater reliability > 0.8). They will also be blinded as to the identity of the trainee performing the procedure, how they were trained (i.e., group) and procedure order.

H₁ It is hypothesised that implementation of PBP training in teaching the robotic suturing of VUA leads to better surgical training outcomes (i.e., lower number of performance errors) when compared to Halsted's method.

Proficiency based progression training for robotic vesico-urethral anastomosis chicken model versus the Halsted's model: a prospective, randomized and blinded clinical trial.

Introduction

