Trainees in the Traditional trained group will be trained according to the traditional approach of 'See one, do one, teach one' principle. Trainees will have a e-learning didactic component (specifically on the anatomy & physiology of the procedure, clinical aspects of the procedure, published evidence etc) which they must complete before training by a procedure expert. On completion of the e-learning module they will complete a summative assessment of their knowledge. They will then be shown how and then trained to suture and tie knots using the robot. The VUA will be demonstrated initially by an expert and who will then proctor the trainees in the same technique for repeated training trials., i.e., repeated practice for a period of time matched to the PBP group.

Students in the PBP trained group will follow the exact same e-learning didactic course as the Traditional trained group but the PBP group will be required to pass a test of procedure knowledge before continuing to the surgical training. Their knowledge will be assessed in a formative and summative fashion. After their initial VUA assessment, procedure-specific and validated procedure metrics will be used to teach the students the steps of the procedure, as well as the correct (and incorrect) way to perform the procedure. The metrics will be used to give them performance feedback with specific advice on how they might improve their performance, i.e., deliberate practice.¹⁷

Both groups of subjects will receive the exact same amount of training and have access the same didactic and training resources. Both groups will also complete a baseline assessment on the chicken model before technical skills training. Assessors, blinded to group membership and procedure order (first or last procedure) will evaluate each student's first and final VUA with the validated chicken anastomosis metrics. They will also assess performance with the GEARS¹⁸ assessment tool (Figure 2). Additionally, the student's satisfaction of the training method will be assessed using a Likert scale 1-5 (Figure 3).

Proficiency Definition: In the study proposed here proficiency levels will be quantified and defined on the objectively assessed performance of surgeons experienced in performing that VUA task being trained. This performance level will be established from the construct validation study of the procedure metrics derived from the procedure characterizations.^{4, 5, 19}

Performance assessments

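### The training-by-order ANOVA names no term for H1 and does not say that order is within-subject; a baseline- and specialty-adjusted end-of-training contrast would settle both at a cost of 3 degrees of freedom

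*Combined protocol and SAP*

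**What the plan says.** The Statistical Analysis paragraph specifies, for approximately normal data, a "two-factor Analysis of Variance where factor one is the type of training subjects received and factor two is the order the task was performed", the two orders being baseline and end of training. For non-normal data it falls back on "Mann-Whitney U for comparison between two independent samples and Wilcoxon signed-rank test". No term is assigned to H1 and no error term is stated.

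H1 (Summary and Hypothesis sections) is that PBP training "leads to better surgical training outcomes (i.e., lower number of performance errors") than Halsted's method. It gives no time point, although the hypotheses about specialties in the same list refer to the end of training.

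The power paragraph is a plain two-group comparison with SD 4, alpha 1% and 16 per group: "Assuming a reduction of ~40% with PBP training (i.e., 16.6 vs 10 errors"). It gives no time point either, and 16.6 is the novice mean from a pilot.

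Two things point to paired data. Under Procedure and training, assessors score each student's "first and final VUA with the validated chicken anastomosis metrics", and the fallback includes a signed-rank test.

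Participants "will be randomized (in equal discipline numbers"), and a note to Figure 1 mentions matching by specialty. In the analysis, specialty appears only in "Specific post hoc statistical contrasts between surgeon groups performance within a training condition".

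On baseline timing, the Baseline Assessment paragraph says: "Prior to the commencement of education and training protocol all subjects from both groups will be assessed". The Summary and Procedure and training sections place it only before skills training.

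**The concern.** A training-by-order ANOVA offers two terms that could be reported as the test of H1, and they estimate different things. The main effect averages baseline and final scores. If the arms start equal, it estimates half the end-of-training difference. The interaction compares changes from baseline. It is a valid test of the end-of-training difference, but it pays for the noise in the baseline score.

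With no term named, the primary p-value could be chosen after the data are seen. If the software is also given two scores per trainee as if they were independent, neither term keeps its nominal 1% level. The plan collects a baseline score and balances specialty, yet uses neither as a covariate in the comparison that matters most.

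**Working it through.** **Inputs from the protocol.** Difference 16.6 − 10 = 6.6 errors; SD 4; alpha 1%; 16 per arm in the power paragraph; 18 per arm randomised.

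**Assumptions.** Two-sided test; the 6.6 errors apply at end of training; equal SD at both times; equal expected baselines; baseline-to-final correlation ρ of 0.2, 0.5 or 0.8. The protocol gives no ρ.

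**The plan's own figure.** With 16 per arm, SE = 4√(2/16) = 1.414 and 6.6/1.414 = 4.67. Two-sided 1% power is 0.982 by normal approximation and 0.966 by noncentral t, against 0.998 stated. The form is therefore a simple two-group comparison. The remaining gap is a separate matter.

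**Standard errors, 18 per arm.** Let s = 4√(2/18) = 1.333.

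- Final-score t-test: s, 34 df. Noncentrality 6.6/1.333 = 4.95.
- Main effect: estimates 6.6/2 = 3.3 with SE s√((1+ρ)/2), 34 df. At ρ = 0.5: 3.3/1.155 = 2.86.
- Interaction (change score): SE s√(2(1−ρ)), 34 df. At ρ = 0.5: 6.6/1.333 = 4.95.
- ANCOVA on baseline and specialty: SE s√((1−ρ²)(1+1/30)), 31 df, where 1/30 is the finite-sample cost of the covariate. At ρ = 0.5: 6.6/1.174 = 5.62.

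**Power by noncentral t, two-sided 1%, 6.6 errors.**

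| Test | 18 per arm, ρ = 0.2 / 0.5 / 0.8 | 16 per arm, ρ = 0.2 / 0.5 |
|---|---|---|
| Main effect | 0.68 / 0.56 / 0.46 | 0.61 / 0.49 |
| Interaction | 0.87 / 0.98 / 1.00 | 0.82 / 0.97 |
| ANCOVA | 0.983 / 0.997 / about 1.00 | 0.96 / 0.99 |
| Final-score t-test | 0.983 throughout | 0.966 throughout |

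If the true difference were 5 errors (an assumption), then with 18 per arm the interaction has 0.60 / 0.84 / 1.00, ANCOVA 0.84 / 0.93 / 1.00 and the final-score test 0.84.

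**Error term.** Simulating the null with 18 per arm and analysing the 72 scores as independent gives the following type I error at nominal 1%. For the main effect it is just under 2%, about 3.5% and about 5.5% at ρ = 0.2, 0.5 and 0.8. For the interaction it is about 0.4% at ρ = 0.2 and lower beyond.

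**Precision of ANCOVA against the interaction.** The SE ratio is √[(1−ρ²)(31/30) / (2(1−ρ))] = 0.79, 0.88 and 0.96 at the three values of ρ. With equal SDs it exceeds 1 only above ρ of about 0.935. With unequal SDs, let k be the final SD divided by the baseline SD. The two tests are equal in large samples when ρk = 1, for example k = 1.25 with ρ = 0.8, or k = 1.5 with ρ = 0.67. ANCOVA's SE is then larger by √(31/30) − 1 = 1.7%, which is its greatest loss against the interaction.

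**Specialty.** Assume it explains 15% of the variance equally at both times. Omitting it puts type I error at 0.3% to 0.5% for the main effect and 0.5% for a final-score test (nominal 1%). The interaction and the specialty-adjusted ANCOVA stay at 1.0%.

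**Baseline timing.** Suppose the baseline followed e-learning and the PBP arm was already 1 error better (an assumption). The interaction would understate the end-of-training difference by 1.0 error and ANCOVA by ρ × 1 = 0.2, 0.5 or 0.8. A final-score contrast would not be affected.

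**The case against.** The strongest reply is that the interaction is the natural term in a baseline-by-end layout. It is valid, and one sentence naming it and declaring order within-subject would close the choice. ANCOVA is then only an efficiency preference: at the planned difference it adds 1 to 2 points at ρ = 0.5 and nothing at 0.8. Its larger advantages need a low ρ or a smaller effect, neither of which is in the protocol. This stands, and it is why that sentence is offered below as the minimum repair. It does not remove the gap, because the sentence is not in the plan.

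Three stronger readings are tempting and are not supported.

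- A reader might infer that the trial was explicitly powered on the end-of-training difference. The power paragraph gives no time point. End of training is the sensible reading, but it is a reading.
- A reader might infer that ANCOVA beats the interaction at all but extreme correlations. That needs equal SDs. If scores spread out more at the end, the two can tie at moderate ρ, and ANCOVA's SE can be about 2% larger.
- A reader might infer that the sections contradict each other on baseline timing. A baseline before all education also comes before skills training, so they are compatible. The later wording merely permits a baseline after e-learning, at which stage only the PBP arm must pass a knowledge test. The Figure 1 diagram, not shown in the text reviewed, may settle the order.

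The specialty argument is secondary: omitting specialty does not inflate type I error, and it leaves the interaction unaffected if specialty shifts both time points equally.

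**Conclusion.** The concern holds in a limited form. The plan leaves open which ANOVA term tests H1 and whether order is within-subject, and it leaves collected baseline and specialty data out of the arm comparison. The open choice is material. At the planned 6.6 errors with 18 per arm, the main effect has power of only 0.46 to 0.68, against 0.87 or more for the interaction. An analysis without a within-subject error term could raise the main effect's false-positive rate to several times the nominal 1%.

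ANCOVA is a modest further improvement. It is clear against the interaction at low ρ, small at 0.5, and absent against a plain final-score test near 0.2. These sizes rest on the assumed ρ, a two-sided test, equal SDs and the end-of-training reading. The documents do not support a claim that the trial is underpowered or that its ANOVA is invalid: a within-subject interaction test would be sound. This is a free improvement that should be made before unblinding.

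**What to change.** 1. Make the primary test of H1 the arm contrast in an ANCOVA of end-of-training error count on training arm, baseline error count and specialty. Report the adjusted difference with its confidence interval.
2. Keep a rank-based comparison of final scores for marked non-normality, and say that it applies to final scores.
3. State in one place, consistently across the Summary, Procedure and training, and Baseline Assessment text, that the baseline VUA precedes e-learning. If it in fact follows e-learning, make the specialty-adjusted final-score contrast primary and the baseline-adjusted one a sensitivity analysis.
4. If the ANOVA is kept, state that order is within-subject and that the training-by-order interaction tests H1.

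The cost is a reworded analysis paragraph and one sentence on timing. Baseline errors and specialty are already collected. The model uses 3 degrees of freedom (one for baseline, two for specialty), taking the residual from 34 to 31 with 36 trainees. The SE loss is at most about 2%.

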Fundamental in creating a proficient robotic surgeon is the acquisition of basic surgical skills, such as suturing and knot tying.¹³ Some training models mimic the real anatomical environment in which a procedure will be performed and provide trainees with the opportunity to learn and practice their skills before starting their practice on real cases in the operating room. Numerous dry-lab, wet-lab, and virtual reality simulation models have been described.¹⁴ The "Venezuelan chicken model" is generally accepted as a optimal model for trainees to learn robotic suturing, anastomosis and knot tying tasks (for all surgical disciplines).¹⁴⁻¹⁶ We will use the Venezuelan chicken model in this study. It has several advantages; it is inexpensive, widely available, easy to prepare, it is a good model for the urethro-vesical anastomosis training, it is possible to introduce a catheter and performing the leakage test, it takes the trainee approx. 20 mins to complete the task. Over the past 12 months ORSI has developed and validated (Delphi consensus and Construct Validity) performance metrics for the task.

This study aims to compare the effectiveness of Halsted's apprenticeship approach to training with the Proficiency Based Progression (PBP) approach for teaching the robotic suturing of a vesico-urethral anastomosis (VUA) on a chicken model.

Methods

Subjects

Robotic naïve urology ($n = 12$), surgery ($n = 12$) and gynecology ($n = 12$) residents ($n = 36$) from the UKU Leuven and University of Gent residency training programs will participate. They will be randomized (using an online randomizer <https://www.random.org/>) to teaching of VUA suturing with either Halsted's ($n = 18$) or the PBP method including procedure-specific, validated metrics ($n = 18$).

Procedure and training

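### The 0.998 power figure sets PBP against pilot novices, not against the trained Traditional arm that H1 names, so it is not supported for the planned comparison

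*Combined protocol and SAP*

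**What the plan says.** The paragraph on statistical power in the Methods starts from pilot data: "A pilot study has shown that novices on average make 16.6 (SD = 4) performance errors on the task". The effect follows: "Assuming a reduction of ~40% with PBP training (i.e., 16.6 vs 10 errors". The SD is kept at 4 and alpha is 1%, with no statement of whether the test is one- or two-sided. The conclusion is that this "with 16 subjects in each group would yield a statistical power of 0.998 for the proposed study".

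H1, in the Summary and under Hypothesis, is that PBP training leads to fewer performance errors than Halsted's method. Under Procedure and training, the Traditional arm completes the same e-learning. Then: "The VUA will be demonstrated initially by an expert and who will then proctor the trainees in the same technique for repeated training trials". This is described as "repeated practice for a period of time matched to the PBP group", and the section adds: "Both groups of subjects will receive the exact same amount of training and have access the same didactic and training resources". Each trainee's first and final VUA are scored, the final one after training in both arms.

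The Subjects section randomises 18 trainees to each arm. The Statistical Analysis paragraph plans a two-factor analysis of variance with type of training as factor one, while "factor two is the order the task was performed", meaning baseline or end of training.

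**The concern.** The comparison that is powered is not the comparison that is planned. The error count of 16.6 describes novices, and the fall to 10 is credited to PBP training. That is a contrast of PBP with novice level. In the trial, novice level corresponds to the baseline VUA. At the final VUA the comparator has had proctored practice for as long as the PBP arm, and some improvement is the purpose of that training. The protocol gives no expected Traditional result after training and does not say that the arm is assumed to stay at 16.6.

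A power of 0.998 tells the reader that a real effect is almost certain to be detected. If the result were not significant, that claim would invite reading it as strong evidence against PBP, when it could reflect a smaller but real difference between two trained arms. The reader also cannot tell what difference between trained arms the trial can detect. Randomisation, endpoint and effect estimate are not affected.

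**Working it through.** **Inputs from the protocol.** Means 16.6 and 10 (difference 6.6), SD 4, alpha 1%, 16 per group in the power paragraph; 18 per arm in Subjects.

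**Assumptions not in the protocol.** The size of the Traditional arm's improvement, the SD in the trained arms, and the correlation rho between baseline and final scores.

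**Method.** Two-group t-test with n per arm. The noncentrality is δ / (SD × √(2/n)) on 2n − 2 degrees of freedom, and power is the noncentral-t probability beyond the critical value.

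**Step 1: the plan's own figure.** With n = 16, the standard error is 4 × √(2/16) = 1.414, so the noncentrality is 6.6 / 1.414 = 4.67 on 30 degrees of freedom.

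| Inputs as stated, 16 per arm, alpha 1% | t-test | Normal approximation |
|---|---|---|
| Two-sided | 0.966 | 0.982 |
| One-sided | 0.983 | 0.990 |

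None gives 0.998. At 18 per arm the t-test gives 0.983 two-sided and 0.992 one-sided. The value 0.998 does appear at 16 per arm with one-sided alpha 5% (0.9982) and at 18 per arm with two-sided alpha 5% (0.9978), but the stated alpha is 1%. At alpha 1%, the t-test reaches 0.998 with 22 per arm one-sided (0.9985; 21 gives 0.9977) or 24 two-sided (0.9983).

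**Step 2: let the Traditional arm improve.** The table uses n = 18, SD 4 and two-sided alpha 1%. The standard error is 4 × √(2/18) = 1.333. The 40% can be read in two ways: PBP ends at 10 whatever the control does, or PBP ends 40% below the trained control.

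| Assumed Traditional improvement | Traditional mean | Difference, PBP at 10 | Power | Difference, PBP 40% lower | Power |
|---|---|---|---|---|---|
| 0% | 16.60 | 6.60 | 0.98 | 6.64 | 0.98 |
| 10% | 14.94 | 4.94 | 0.83 | 5.98 | 0.95 |
| 20% | 13.28 | 3.28 | 0.41 | 5.31 | 0.89 |
| 30% | 11.62 | 1.62 | 0.08 | 4.65 | 0.77 |

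At 16 per arm, the last three rows give 0.765, 0.351 and 0.068 on the first reading, and 0.921, 0.834 and 0.701 on the second.

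**Step 3: detectable difference at 18 per arm, two-sided alpha 1%.**

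| SD | 80% power | 90% power |
|---|---|---|
| 3 (assumed) | 3.59 | 4.06 |
| 4 | 4.79 | 5.41 |
| 5 (assumed) | 5.99 | 6.76 |

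With SD 4, power falls below 80% once the Traditional arm improves by more than (6.6 − 4.79) / 16.6 = 11% on the first reading, or 1 − 4.79 / (0.4 × 16.6) = 28% on the second. It falls below 50% at about 18% and 46%.

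**Step 4: the planned ANOVA.** With two time points, the training-by-time term is equivalent to a t-test on change. If the SD is 4 at both times, the SD of change is 4 × √(2(1 − rho)). At rho = 0.5 this is 4, so the figures above apply unchanged. With 10% Traditional improvement and 18 per arm:

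| Assumed rho | PBP at 10 | PBP 40% lower |
|---|---|---|
| 0.3 | 0.656 | 0.847 |
| 0.5 | 0.828 | 0.954 |
| 0.7 | 0.976 | 0.998 |

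With the stated difference of 6.6 and 16 per arm, this term reaches 0.998 (two-sided) at rho of about 0.68. The protocol states no rho.

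**The case against.** The pilot is not described. Its novices could have been traditionally trained, or the sponsor could have set the Traditional arm at 16.6 on purpose. This cannot be excluded from the documents. Still, the trial's own trainees are robotic-naive and the reduction is attributed to PBP, so untrained is the natural reading. If another meaning was intended, one sentence would settle it, and that sentence is missing.

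The improvements of 10% to 30% are invented, and the low values (0.41, 0.08) arise only if PBP is fixed at 10. That is right. If the 40% is relative to the trained control, power stays at 0.77 or above through 30% improvement. The table shows how much depends on an unstated assumption; it does not estimate the trial's power.

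Holding the SD at 4 may be pessimistic for PBP, since that arm trains to a benchmark, which could narrow its spread. This is possible, but the documents do not settle it.

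The planned ANOVA could be more powerful than a t-test, and could reach 0.998. This stands, but only at a correlation that the protocol never gives; at rho 0.3 power is lower than the t-test's.

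Finally, 0.97 against 0.998 would change no decision, and calculating with 16 while randomising 18 is conservative. Both points are fair. The arithmetic gap is secondary, although it does mean a type II error of 3.4% (two-sided t-test) where 0.2% is claimed. The 16 against 18 needs a word of explanation and is not a fault in itself.

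**Conclusion.** The concern holds and should be fixed. The claimed 0.998 is unsupported for PBP against a trained Traditional arm, because the only comparator mean is that of pilot novices and no end-of-training Traditional mean or SD is given. As a secondary point, neither a t-test nor a normal approximation gives 0.998 from the stated inputs at alpha 1%; the range is 0.966 to 0.990.

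Confidence is high that the figure is unsupported. The documents do not allow the conclusion that the trial is underpowered: that depends on how far traditional training lowers errors, what the 40% refers to, the SD after training and the baseline-final correlation.

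**What to change.** Delete 0.998 and restate power for PBP against Traditional at the end of training, with the planned 18 per arm. The paragraph should give:

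- the assumed Traditional mean and SD after training, with their source, and who the pilot novices were and when they were assessed;
- whether the 40% is relative to novices or to trained controls;
- whether alpha is one- or two-sided;
- a short table of power over a range of Traditional means.

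Suggested wording: *With 18 per arm, SD 4 and two-sided alpha 1%, a two-group t-test has 80% power for a difference of 4.8 errors and 90% power for 5.4.* Add that these are t-test figures, because power for the two-factor ANOVA needs the correlation between baseline and final scores, which should be stated if it is known.

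The cost is one reworded paragraph and a small table. The stated power becomes less favourable. Enrolment does not change.
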